At enrollment, primary caregivers will be interviewed to assess demographic information, medical history, and detailed contact information for the child. Medical records will also be used to abstract information from the hospitalization (including presenting diagnosis, medical management, length of stay, procedures performed, relevant medical history, physical examination, and laboratory data). All enrolled participants will undergo a physical examination performed by the study clinician, including measurement of height/length, weight, and mid-upper arm circumference (MUAC). The height, weight, and MUAC of the caregiver will also be collected. If laboratory results are not available from the hospitalization, HIV testing will be performed as indicated by Kenya NASCOP Guidelines (HIV testing should be performed in all children presenting to a healthcare facility).[60] Any child newly diagnosed with HIV will be referred to the HIV Care Clinics at the study sites for follow-up care and treatment. Because enrollment procedures may take up to an hour or more and on days of multiple enrollments, enrolled caregivers/children may have to wait to complete the enrollment procedures, caregivers will be provided with 200-500KSH (\$2-5USD) to cover the cost of their transportation home.

Specimen collection

Enrollment, 90-days, and 6 months

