*Aim 2b. To determine whether empiric administration of azithromycin at hospital discharge increases risk of antimicrobial resistance in commensal *E. coli* and pneumococcal isolates from treated children and their household contacts.* Among children and adult household contacts in whom commensal *E. coli* and/or *S. pneumoniae* are isolated, we will compare the proportion of β -lactam or macrolide resistance, or both, between randomization arms and Contact Cohorts for each arm, at 90-days and 6 months using GEE with a

Poisson link and exchangeable correlation structure. A chi-squared test will be used to determine whether the association between intervention arm and antimicrobial resistance wanes over time. Because the likelihood of having a bacterial pathogen isolated may depend on baseline factors, including intervention arm, we will conduct secondary analyses utilizing propensity scores to account for the potential differential likelihood of having antimicrobial susceptibility testing performed, which will allow us to make inference to the entire study population and their contacts.

Aim 3. To identify correlates and intermediate markers of post-discharge mortality and hospital-readmission among hospitalized Kenyan children. Enrollment hospital admission diagnosis, indicators of malnutrition, age, and randomization arm will be assessed in a multivariable Cox regression model to identify correlates of the primary endpoint of death and/or hospital-readmission independent of the treatment effect. In addition, Cox regression models will also be built for correlates of mortality and correlates of re-admission individually to understand distinct cofactors for each of these outcomes.

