A short course of azithromycin given to children with recent severe illness being discharged from hospital may optimize benefit while reducing both individual and population level risks. Azithromycin may reduce post discharge morbidity and mortality through infection-related mechanisms such as treating undiagnosed, incompletely treated or nosocomial infections, or by protecting against new or recrudescent infections that occur during recovery. Azithromycin may also act through non-antimicrobial pathways by anti-inflammatory and/or immune-modulatory effects.

Objectives

Aim 1. To compare rates of **re-hospitalization and mortality** in the 6 months following hospital discharge among Kenyan children receiving 5-day azithromycin vs. placebo.

Hypothesis: The provision of a 5-day course of azithromycin provided at discharge will reduce hospital re-admission and death within the 6 months following discharge, as compared to placebo.

Aim 2a. To evaluate possible **mechanism(s)** by which azithromycin may affect morbidity and mortality, by comparing **reasons for re-hospitalization and prevalence of pathogen carriage** between the randomization arms.

Hypothesis: Children treated with azithromycin will experience fewer hospitalizations due to diarrhea, acute respiratory infection, and malnutrition, and will be less likely to have respiratory and gastrointestinal carriage of potentially pathogenic organisms, as compared to children treated with placebo in the 6 months following hospital discharge.

Aim 2b. To determine whether empiric administration of azithromycin at hospital discharge **increases risk of antimicrobial resistance** in commensal *Escherichia coli* (*E. coli*) and *Streptococcus pneumoniae* (*S. pneumoniae*) isolates from treated children and their household contacts.

*Hypothesis: Isolates of commensal *E. coli* and *S. pneumoniae* from children treated with azithromycin and their household contacts will have higher levels of macrolide and β -lactam resistance, compared to the placebo group, after 90 days of follow-up, but resistance in the 2 arms will be similar by 6 months.*

Aim 3. To identify **correlates and intermediate markers of post-discharge mortality and hospital readmission** among hospitalized Kenyan children.

Hypothesis: Children younger in age, with higher levels of bacterial pathogen carriage, immune dysfunction, and malnutrition will experience more frequent re-hospitalizations and deaths.

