Analysis of primary outcomes will be by modified intention-to-treat (mITT). The mITT population will include all randomized children according to the treatment they were randomized to receive but will exclude those who were deemed ineligible, post-randomization. In per-protocol analyses (secondary to the mITT), we will compare treatment effects in groups defined by self-reported adherence to the 5-day course of azithromycin. Per protocol analyses will also exclude children who were ineligible, those who were lost to follow-up, and those who withdrew consent.

SECTION 5. TRIAL POPULATION

Screening Data

The total number screened will be reported along with summary of reasons for exclusion into the trial.

Eligibility

Children age 1 to 59 months old who weigh at least 2 kg and have been hospitalized and subsequently discharged from hospitals in Kisii or Homa Bay County for conditions other than trauma, injury, poisoning, or a birth defect, will be eligible for the RCT (Aim 1). We will exclude children in whom azithromycin is contraindicated (children taking or prescribed other macrolide antibiotics, such as erythromycin or clarithromycin, or the protease inhibitor lopinavir); those with a known macrolide allergy, those who do not plan to remain in the study site catchment area for at least 6 months, those without a legal guardian or a legal guardian does not provide consent, those with a twin is eligible and enrolled in the trial on the same day, those that are being referred to another facility, and those with a caregiver who is unwilling to participate in contact cohort if selected (willing/able to provide a stool and nasopharyngeal sample at enrollment, 90 days and 6 months of follow-up if randomized to the Contact Cohort).

Recruitment

Per CONSORT guidelines, we will report the number of individuals who:

1. Underwent screening
2. Met inclusion criteria
3. Did not meet inclusion criteria (and reasons)
4. Enrolled in the study and were randomized

5. Were included in the mITT
6. Were included in the per-protocol population

Withdrawal/Follow-Up

Level of withdrawal (e.g. from intervention and/or from follow-up)

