Prescribed antibiotics at discharge			
Nutritional, HIV, and Vaccine Status			
Breastfeeding status (in first 6 months of life)			
Exclusively breastfed			
Partially breastfed			
Never Breastfed			
Unknown			
Stunted (HAZ < -2)			

Underweight (WAZ < -2)			
Acute Malnutrition			
Severe (WHZ < -3 or MUAC <11.5cm or edema)			
Moderate (-3 ≥ WHZ < -2 or 11.5 ≥ MUAC <12.5cm)			
HIV-status			
HIV- infected			
HIV-exposed, uninfected			
HIV-exposed, unknown infection status			
HIV status unknown			
Received all age-appropriate vaccines			

SECTION 6. ANALYSIS

Outcome Definitions

Primary study end-points:

1. **Deaths** will be ascertained by study staff either through community health workers, hospital staff, or determined at follow-up visits. Date of death will be ascertained from the following (in order of prioritization): death certificate, hospital record, caregiver report
2. **Re-hospitalization** will be assessed by questionnaire at day 90 and 180 follow-up visits and medical record review. In cases when both sources are available, information from the medical record will be considered the gold standard. A hospitalization will be defined as an overnight stay, including situations where a child is admitted in the middle of the night (even if after midnight) and discharged the subsequent morning. Re-hospitalizations that are a continuation of management from the previous hospitalization (such as elective blood transfusion) or that occur during enrollment procedures, due to a clinical deterioration post-discharge, will be excluded from the analysis. To operationalize these exclusions, we will exclude re-hospitalizations that occur <2 hours after administration of the study medication and those re-hospitalizations that occur as a result of the child being advised to seek further care for a blood transfusion due to a lack of blood availability at the enrollment facility.
3. **Loss to follow-up** will be defined as non-attendance at both follow-up visits despite up to one month of active tracing and no clear evidence of death.
4. **Death or re-hospitalization** (combined) is the primary endpoint.

Secondary end-points:

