Outcome	Azithromycin-treated group (N=)			Placebo-treated group (N=)			Effect Estimate		
	n	Person-time	Incidence rate (/100)	n	Person-time	Incidence rate (/100)	Hazard ratio	(95% CI)	p-value
Death or re-hospitalization									

In subgroup analyses, we will compare treatment effects in children whose caregivers report no additional antibiotic use over follow-up and separately, who report no additional azithromycin use specifically and in subsets of children defined by the following baseline characteristics: age, county of recruitment, HIV-exposure status, nutritional status, and discharge diagnosis. We will not conduct formal testing of interaction in these analyses. We will report within sub-group p-values but interpret as secondary sub-group analyses. Also in secondary analyses, we will allow more than one hospitalization and model the incidence of re-hospitalization by randomization arm using Anderson-Gill models.

We will report causes of death (and predisposing conditions in those deaths) by randomization arm (without statistical testing) as presented in Table 4.

Table 4. Causes of death by randomization arm

	Azithromycin-treated group (N=)	Placebo-treated group (N=)
Primary cause		
LRTI/Pneumonia		
Diarrhea		
Malaria		
Tuberculosis		
Other Infection		
Other non-infectious		
Predisposing conditions		
HIV		
Sickle cell disease		
Confirmed acquired condition		
Confirmed congenital condition		
None		

Statistical Analysis of Secondary Aims

In addition to the primary aim of the study to determine whether a short-course of azithromycin reduces risk of post-discharge morbidity and mortality, secondary aims include determining potential mechanisms and intermediate markers of an intervention effect, the impact of the antibiotic course on antimicrobial resistance in gut and nasopharyngeal pathogens, and correlates of post-discharge morbidity and mortality. The below tables outline these planned analyses.

Aim 2a. To evaluate possible mechanism(s) by which azithromycin may affect morbidity and mortality, by comparing reasons for re-hospitalization and prevalence of pathogens between the randomization arms.

Population	Dependent variable	Independent Variable	Covariates	Statistical model
------------	--------------------	----------------------	------------	-------------------

Reasons for re-hospitalization				

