1. Randomly selected adult contacts who are participating in AMR sub-study 2. Random subset of adult AMR sub-study participants in whom S. pneumoniae	Prevalence of resistance to azithromycin. In secondary analyses, prevalence of amoxicillin/ K clavulanate, ampicillin, chloramphenicol, clarithromycin, erythromycin, penicillin, trimethoprim-sulfamethoxazole @ 0, 3, & 6 months	Randomization arm (ITT primary and per-protocol secondary)	1) Site 2) Adjusting for imbalanced baseline factors & baseline presence of resistance 3) Adjusting for propensity score made up of factors predictive of likelihood that S. pneumoniae is isolated	GEE with Poisson link & exchangeable correlation structure. Wald tests to compare between arms and to test for time-interaction (waning in resistance from 3 to 6 months in AZM arm)

Aim 3. To identify correlates and intermediate markers of post-discharge mortality and hospital-readmission among hospitalized Kenyan children.

Population	Dependent variable	Independent Variable(s)	Covariates	Statistical model
All enrolled children	Time to death or re-hospitalization	• Child nutritional status • HIV status (child & mother) • Vaccination status • Abnormal discharge • Discharge diagnosis • Length of hospital admission • Infection presence at discharge • Antibiotic resistance at discharge • Feeding practices • Socio-economic status • Caregiver education and nutritional status	Randomization arm, site	Cox proportional hazards
	Time to re-hospitalization		Randomization arm, site	Cox proportional hazards and Andersen-Gill for >1 hospitalization
	Time to death		Randomization arm, site	Cox proportional hazards

Aim 4. To determine the cost-effectiveness of post-discharge administration of a 5-day course of azithromycin in settings of varying antibiotic use, re-hospitalization rates, and mortality rates.

Costs analysis: We will assess the costs of all supplies, services and equipment necessary to implement the intervention (direct medical costs). The perspective will be that of the healthcare provider, i.e. Kenya's Ministry of Health. Using WHO guidelines and its ingredients approach, we will quantify the resources and associated unit costs required to deliver a 5-day course of azithromycin, organized in Version 5.0

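### The SAP's Aim 3 table leaves out age, against the protocol and the SAP's own hypothesis; separately, the moderate-malnutrition bounds in SAP Table 2 are reversed

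*SAP*

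**What the plan says.** **Aim 3 and age**

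- Protocol, Data Analysis, Aim 3: admission diagnosis, "indicators of malnutrition, age, and randomization arm will be assessed in a multivariable Cox regression model".
- SAP Section 2, Objectives, Aim 3 hypothesis: "Children younger in age, with higher levels of bacterial pathogen carriage, immune dysfunction, and malnutrition will experience more frequent re-hospitalizations and deaths".
- SAP Section 6, Aim 3 table: eleven independent variables are listed, among them nutritional status, HIV status, vaccination, discharge diagnosis, feeding practices and socio-economic status. Age is not one of them. For each outcome (death or re-hospitalization, re-hospitalization, death) the covariate cell reads "Randomization arm, site". The models are Cox throughout, plus Andersen-Gill for repeated hospitalizations.
- SAP Section 1, revision history: version 2.0 added the analysis plan for the secondary aims, and version 4.0 added site to the ITT model. No entry mentions age.

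**Acute malnutrition**

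SAP Section 5, Table 2 has two rows: "Severe (WHZ < -3 or MUAC <11.5cm or edema" and "Moderate (-3 ≥ WHZ < -2 or 11.5 ≥ MUAC <12.5cm".

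**The concern.** Aim 3 exists to identify correlates of post-discharge death and readmission. If the SAP table is followed, the first correlate in its hypothesis is neither estimated nor tested. The remaining associations are then reported with adjustment for arm and site alone. Any correlate that varies with age could carry part of an age effect, and a reader could not tell from the planned output whether it does. The documents also leave two different Aim 3 models on record, so an analyst would have to choose between them.

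The Table 2 slip is smaller. It is the only written definition of moderate acute malnutrition in the SAP, and Table 2 is also the named source of candidate confounders for the secondary adjusted Cox model. Code that follows the printed inequalities would give a moderate class that is almost empty once severe children are removed.

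**Working it through.** **1. Age in Aim 3, set side by side**

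| Source | Age included? | Other adjustment |
|---|---|---|
| Protocol, Data Analysis, Aim 3 | Yes, in the multivariable Cox model | Admission diagnosis, malnutrition indicators, arm |
| SAP Section 2, Aim 3 hypothesis | Yes, named first | Not applicable |
| SAP Section 6, Aim 3 table | No, in neither column | Arm, site |

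The SAP does not say whether the listed correlates enter one at a time or together. It makes no difference here, because age is absent either way.

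**2. Do the documents give reason to think age matters?**

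Protocol Table 1a summarises eight post-discharge mortality cohorts. Seven list an age factor. Six of these point to younger children; the seventh names 24–35 months in a cohort aged 3 months to 3 years. Four cohorts list both an age factor and a nutritional one. The cohort of children aged 1–23 months with diarrhea lists age under 6 months together with malnutrition.

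This evidence has a limit. It concerns death. Protocol Table 1b, on re-admission, gives no risk factors, and at the conservative end of the protocol's assumptions the 22.5% composite is 20.5% re-hospitalization plus 2% death.

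**3. Can the confounding be sized?**

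Omitting age distorts another correlate's hazard ratio only if age is related to the outcome and also to that correlate. The first condition has support for mortality. For the second the documents give no data: there is no age distribution, no cross-tabulation of age with any correlate, and no age hazard ratio. No figure can be derived.

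**4. The moderate row, read literally**

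- WHZ limb: −3 ≥ WHZ and WHZ < −2. The first condition implies the second, so this is WHZ ≤ −3.
- MUAC limb: 11.5 ≥ MUAC and MUAC < 12.5. By the same logic, this is MUAC ≤ 11.5 cm.

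The overlap with severe (edema left aside) can be counted on a grid of WHZ from −5 to 2 and MUAC from 9 to 17 cm in steps of 0.1, which has 71 × 81 = 5751 points:

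- Moderate as written: 21 × 81 + 26 × 71 − 21 × 26 = 3001
- Severe: 20 × 81 + 25 × 71 − 20 × 25 = 2895, all of them also moderate as written
- Moderate but not severe: 3001 − 2895 = 106, all exactly on WHZ = −3 or MUAC = 11.5

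Grid points are not children, so these counts show the logic and are not a prevalence. Two examples make the gap concrete. A child with WHZ −2.5 and MUAC 13.5 cm, or with WHZ −1 and MUAC 12.0 cm, falls in neither class as written. Both become moderate once the lower-bound signs are turned, and the classes no longer overlap once severe children are excluded.

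**The case against.** **On age.** The SAP says its tables outline the planned analyses, its hypothesis still names younger age, and the protocol still specifies age in the model. No revision entry records a decision to remove it. This may therefore be an omission in a table, with no intention to drop age. That is fair, and it is why the point is a reconciliation between documents. It does not remove the need, because the table is the SAP's specific statement of the Aim 3 models and it leaves age out for every outcome.

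**On the signs.** The severe row makes the intent plain, the rows sit in a descriptive shell table, and Table 2 variables enter only a secondary model that depends on observed imbalance and a change of more than 10% in the hazard ratio. All of this stands, so the sign correction is minor.

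**Stronger readings that a reader might infer**

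- *The fixed MUAC cut-offs are invalid in the youngest children, so malnutrition partly measures young age.* Eligibility does cover "Children age 1 to 59 months old who weigh at least 2 kg", and MUAC is measured in all of them. But the documents give no age range for these cut-offs and no MUAC values by age, so the claim would rest on outside knowledge. The Aim 3 table also does not say that nutritional status means the acute-malnutrition rows; Table 2 also holds stunting and underweight, which are z-score based.
- *The nutritional-status subgroup is biased by age.* The planned subsets are "age, county of recruitment, HIV-exposure status, nutritional status, and discharge diagnosis". Within each, the comparison is between randomised arms, so age does not confound the treatment effect. Overlap between the age and nutrition subgroups is not an error.
- *A specific false hazard ratio for malnutrition.* Every input would have to be assumed, and plausible inputs include values that give no inflation.

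**Conclusion.** The SAP's Aim 3 table contradicts the protocol's Aim 3 model and the SAP's own hypothesis by leaving out age, and no reason is recorded. As written, the age association is not estimated and the other correlates are not adjusted for age. The conclusion rests only on comparing the documents' variable lists. That age matters is supported by the protocol's cited mortality cohorts; its bearing on readmission, and the size of any confounding, cannot be determined from the documents.

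The reversed lower bounds in the moderate row are certain as a matter of logic, probably typographical, and of small consequence. The two points are independent of each other. Neither touches the primary mITT Cox model, which contains arm and site.

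**What to change.** 1. In the SAP Aim 3 table, add age as an independent variable and as a covariate for the other correlates, for all three outcomes, including the Andersen-Gill model for repeated hospitalizations. State the form in advance: the four Table 2 bands or a continuous term.
2. In SAP Table 2, write the moderate class as −3 ≤ WHZ < −2 or 11.5 ≤ MUAC < 12.5 cm, and not severe. This agrees with the severe row as it stands.

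The cost is SAP wording. Age is a Table 2 variable, and the protocol already provides for "measurement of height/length, weight, and mid-upper arm circumference (MUAC") at enrollment. Age adds three parameters if banded and one if linear. On the protocol's Aim 3 inputs (1400 × 0.80 = 1120 children; 1120 × 0.225 = 252 events) that is a small burden for the composite. For death alone, the protocol's 2–15% range gives about 22 to 168 deaths (1120 × 0.02 and 1120 × 0.15), so at the low end a single continuous term would be more economical than bands.
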